9.2.2 Potential risks

- The clinical trial may require more time and hassle than a non-clinical trial treatment such as visits to the clinical trial site and potential waiting period prior to investigator's assessment.
- There may be possible risk of burning and stinging sensation on scratch wounds, irritation, and allergic reaction which is common of topical applications.

9.2.3 Risk Benefit Assessment

There is minimal risk from the IP and study procedures are non-invasive. Study findings shall potentially greatly improve treatment outcomes. The expected benefit outweighs the minimal risk to subjects and thus this study should be supported. All parties are insured by trial insurance provided and paid for by the sponsor.

9.2.4 Informed Consent/Assent Process

All interested party shall be informed and briefed of the study during the advertisement period by the investigator team. All parents will be properly informed and allowed a fixed time period to consider and inquire prior to consent. Two consents will be taken from children above 7 years where they will also be properly informed and allowed a fixed time period to consider and inquire prior to consent. All participation is strictly voluntary based. An appointment will be made where the patient information sheet will be provided and explained to them. If they are willing to participate, the consent forms will be signed and dated. If they need to, they are allowed to take the information sheet home to consult with their family members, and another day for getting consent arranged.

9.2.5 Privacy and Confidentiality

All subjects' personal data will be kept confidential. Subject's names will be kept on a password-protected database and will be linked only with a study identification number for this research. The identification number instead of patient identifiers will be used on subject data sheets. All data will be entered into a computer that is password protected. On completion of study, data in the computer will be copied to CDs and the data in the computer erased. CDs and any hardcopy data will be stored in a locked office of the investigators and maintained for a minimum of three years after the completion of the study. The CDs and data will be destroyed after that period of storage. Subjects will not be allowed to view their personal study data, as the data will be consolidated into a database. Subjects can write to the investigators to request access to study findings

9.2.7 Publication Policy

No personal information will be disclosed and subjects will not be identified when the findings of the survey are published.

9.2.8 Termination of Study

The sponsor may decide to terminate the study at any time. Subjects will be informed if the study is terminated and follow-up visits will be arranged if needed.

10. Statistical Analysis Plan

All data obtained at baseline will be given a coded ID-number before they are used in further statistical analyses.

- 10.1 The data analysis will be performed using Minitab 16. Descriptive date will be expressed as mean ± standard deviation (SD) unless otherwise stated. A value of P < 0.05 is considered statistically significant.
- 10.2 Prior to the statistical analysis, investigator needs to determine whether intention-to-treat analysis or modified intended-to-treat analysis is used for the statistical analysis. As well per-protocol analysis also can be carried out for comparison purpose. In

addition, the distribution of the data needs to be checked if it is following Gaussian distribution.

- 10.3 Comparison of SCORAD index between baseline and follow-up visits (if data is following Gaussian distribution, ANOVA will be used. If it is not following Gaussian distribution, Kruskal-Wallis test will be used.)
- 10.4 Comparison of POEM between baseline and follow-up visits (if data is following Gaussian distribution, ANOVA will be used. If it is not following Gaussian distribution, Kruskal-Wallis test will be used.)
- 10.5 Comparison of DLQI between baseline and follow-up visits (if data is following Gaussian distribution, ANOVA will be used. If it is not following Gaussian distribution, Kruskal-Wallis test will be used).
- 10.6 Correlation between SCORAD index with POEM or DLQI at baseline will be analysed using correlation coefficient (r) test. The cut-off values to interpret the correlations were as follows: < 0.5 = no correlation, > 0.5 = correlation, > 0.7 = high correlation. (If it is following Gaussian distribution, Pearson correlation will be used. If it is not following Gaussian distribution, Spearman correlation will be used)

11. Expected outcome

- REMDII[®] Sensitive will be effective in improving mild-to-moderate atopic dermatitis in children based on the positive changes of IGA score and SCORAD.
- Clinician-assessed IGA and SCORAD is directly correlated with patient-assessed SCORAD after 12 weeks of treatment using IP.
- IDLQI of subjects significantly improved compared to baseline as well as vehicle group.
- REMDII[®] Sensitive improves skin properties (HR-USI, color & TEWL) in children.
- REMDII[®] Sensitive will has no negative side effects on children with mild-tomoderate atopic dermatitis.

12. Gantt chart & milestone

Gantt chart

Activities	2019								2020								
	5	6	7	8	9	10	11	12	1	2	3	4	5	6	7	8	9
Ethical clearance																	
Recruitment																	
Screening																	
Trial study																	
Data collection &																	
analysis																	
Presentation &																	
publication																	

Milestone

Stage 1, review of medical records – 0.5 months
Stage 2, data collection and data analysis – 1-12 months
Stage 3, presentation and publication - 6-18 months
The participation duration for each subject is *3 months*.

13. Ethical consideration

All procedures will be conducted in compliance with ethical principles outlined in the Declaration of Helsinki and Malaysian Good Clinical Practice Guideline and will be well explained to subjects prior to signing of subject informed consent. Any subjects could withdraw at any time during the clinical trial, even without explanation.

The study involves no greater than minimal risk as the probability and magnitude of harm or discomfort anticipated in the research are not greater in and of themselves than those ordinarily encountered in daily life or during the performance of routine physical or psychological examinations or tests. Vulnerable group involves baby and children. All subjects will involves permission of one parent, while informed consent will also be obtained from children above 7 years old.

14. Declaration of conflict of interest

The investigators declare they have no conflict of interest. [name]. [name], [name] and [name] [name] are representatives from Lipidware Sdn. Bhd.

15. Honoranium and incentives to respondents

- Token of appreciation

Free moisturisers will be given to respondents that completes the 12 weeks study for the period of one year (including the study period).

- Cost of transportation

All subjects will be provided RM30 each, for every visits, as incentive.

16. Other ethical review board approval (if applicable)

N/A

17. References

- Arellano, F. M., Arana, A., Wentworth, C. E., Fernández-Vidaurre, C., Schlienger, R. G., & Conde, E. (2009). Lymphoma among patients with atopic dermatitis and/or treated with topical immunosuppressants in the United Kingdom. *Journal of Allergy and Clinical Immunology*, *123*(5), 1111-1116. e1113.

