9.1 Study Type and Design

9.1.1 Study design

A Phase 2, single arm, open label, single-centre trial will be conducted at Hospital Pengajar UPM, [name] and Lipidware Sdn. Bhd. Participants fulfilling the eligibility criteria will be selected. Each participant will be examined for signs and symptoms of AD before and after using REMDII[®] Sensitive. Figure 2 shows the outline of the study.

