9.1.8 Sample Size

Sample size calculations were performed according to Cheon et al. (2013) using the following formula, where the mean difference and standard deviation of the scoring atopic dermatitis (SCORAD) index will be 10 and 13.576, respectively.

$$n = \frac{2(z_{\alpha/2} + z_{\beta})^2 \sigma^2}{(\mu_c - \mu_t)^2} = \frac{2 \times (1.96 + 0.84)^2 \times 13.576^2}{10^2} = 28.932$$

Using 80% power, a 5% significance level, and a 10% dropout rate, the required sample size will be corrected to approximately 33 participants for a group. Therefore, a total of 33 participants will be needed for this trial.

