9.1.10 Study Visits and Procedures

- 9.1.10.1 Subjects who are eligible to take part in this trial will need to attend to the study site for a total of 5 compulsory visits, as illustrated in Fig. 3.
- 9.1.10.2 During the screening/baseline visit, it will take about 1 hours where the investigators will take note of the subjects conditions for evaluation of study acceptability.
- 9.1.10.3 Prior to any baseline measurement, the correct usage of the cream will be explained by the investigator and the investigator's team. Subjects will be required to apply at least 1 fingertip unit to 2% body surface area. The subjects will receive treatment with the IP for topical application for 3 times a day for 12 weeks (according to the guideline that emphasize the important of using sufficient emollient).
- 9.1.10.4 Subjects will be provided with non-soap-based shower product (REMDII® Calming Body Wash, Malaysia) for subject's shower purpose throughout

the study. Subjects should avoid the usage of soap-based products throughout the study.

- 9.1.10.5 Subjects will also be provided with a diary, for recording of any application of rescue treatment and deviation from the study protocols.
- 9.1.10.6 Subjects who have flare up, will be managed using hydrocortisone 1% cream for a duration of 7 days. Those who are not responding to hydrocortisone end of 7 days will be prescribed with clobetasone butyrate 0.05% cream for additional 7 days. Those who doesn't respond to the treatment shall be withdrawn. However, subjects need to record the application in the provided diary. As well, any deviation or illness that occurs during the study will need to be recorded in the same diary as well.
- 9.1.10.7 Those who acquired secondary bacterial infection will be treated with a week of cloxacillin (50-100mg/kg/day po in 4 divided dose). For those who are above 20kg, will receive the usual adult dose.
- 9.1.10.8 In patients with penicillin allergy will be given a week of erythromycin ethylsuccinate at a dose of 30mg/kg/day in divided dose (up to a max 2gm/day).
- 9.1.10.9 Patients who have eczema herpeticum will received a week of oral acyclovir, in which subjects 1 month till 2 years will receive 100mg 5×/day; while subjects age 2 to 12 years old will received 200mg 5×/day dosage.
- 9.1.10.10After the explanation of the "Dos and Don'ts" to the guardians/parents, baseline measurement of atopic dermatitis severity of subjects using SCORAD index will be conducted.

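### Sections 10.3 to 10.5 name Kruskal-Wallis, and an ANOVA without a child term, for repeated measurements on the same children; the tests are conservative and can hide a real improvement

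*Protocol*

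**What the plan says.** Section 9.1.1 describes the design: "A Phase 2, single arm, open label, single-centre trial will be conducted". It adds that "Each participant will be examined for signs and symptoms of AD before and after using" the product. Section 9.1.10.1 has eligible children "attend to the study site for a total of 5 compulsory visits". Baseline and follow-up values therefore come from the same children.

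Section 10.3 gives the SCORAD test: "Comparison of SCORAD index between baseline and follow-up visits (if data is following Gaussian distribution, ANOVA will be used". The alternative is: "If it is not following Gaussian distribution, Kruskal-Wallis test will be used". Sections 10.4 and 10.5 apply the same pair of tests to POEM and DLQI. Section 10.1 sets the threshold: "A value of P < 0.05 is considered statistically significant". The protocol names no paired, repeated-measures, Friedman, signed-rank or mixed-model method.

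Section 9.1.8 sizes the trial on SCORAD, with a difference of 10 and an SD of 13.576: "Using 80% power, a 5% significance level, and a 10% dropout rate". The result is 28.932, raised to 33 children.

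**The concern.** Kruskal-Wallis and one-way ANOVA treat each visit as a separate sample of unrelated children. Stable differences between children then stay in the error term, although a before-after comparison exists to remove them. The p-values no longer have their nominal meaning. With positive within-child correlation they are too large, so the test rejects less often than 5% when nothing has changed and less often than it could when the children have improved.

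These are the only before-after tests the protocol states, and one of them concerns SCORAD, the variable that sized the trial. At stake is a real improvement reported as non-significant.

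**Working it through.** **Inputs.** Difference 10, SD 13.576, two-sided 5%, 80% power and 10% dropout (9.1.8); up to five values per child (9.1.10.1). The within-child correlation ρ is not in the protocol. It is assumed equal between all pairs of visits and shown at 0.3, 0.5 and 0.7. The shape of the change over time is not given either, so three shapes are shown.

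**The plan's own figure.** n = 2(z₀.₉₇₅ + z₀.₈₀)² × 13.576² / 10² = 28.932 with unrounded z values (28.899 with the printed 1.96 and 0.84). Rounded up this is 29, and 29/0.9 = 32.2, hence 33. The figure reproduces. The calculations below use the 29 children left after dropout.

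**Why the tests are conservative.** Let σ² = 13.576² = 184.3. If nothing changes over time, the mean square for visits has expectation σ²(1 − ρ). The one-way error mean square has expectation σ²; the repeated-measures error mean square has σ²(1 − ρ). The one-way F ratio therefore centres near 1 − ρ instead of 1, for example near 0.5 at ρ = 0.5.

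For two time points the SD of the change is 13.576 × √(2(1 − ρ)) = 16.06, 13.58 and 10.52 at ρ = 0.3, 0.5 and 0.7. The independent-samples test uses 13.576 × √2 = 19.20. Its true type I error is then roughly 2Φ(−1.96/√(1 − ρ)):
- ρ = 0.3: 2Φ(−2.34) = 1.9%
- ρ = 0.5: 2Φ(−2.77) = 0.6%
- ρ = 0.7: 2Φ(−3.58) = 0.03%

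**Simulated type I error, nominal 5%** (normal data, n = 29, ρ = 0.3 / 0.5 / 0.7)

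| Setting | One-way ANOVA | Repeated-measures ANOVA |
|---|---|---|
| 5 visits | 1.1 / 0.2 / 0.01% | 5.2 / 4.7 / 5.1% |
| 2 time points | 2.3 / 0.7 / 0.1% | about 5% |

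Kruskal-Wallis behaves almost exactly as one-way ANOVA does here.

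**Simulated power at a difference of 10** (same settings; repeat runs differ by about a percentage point)

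| Course of SCORAD | One-way ANOVA | Kruskal-Wallis | Within-child analysis |
|---|---|---|---|
| Linear fall over 5 visits | 67 / 64 / 62% | 64 / 60 / 58% | 85 / 96 / 99.8% |
| Full fall by first follow-up, then held (range over ρ) | 80-81% | 76-77% | 94-100% |
| Baseline against one follow-up | 82 / 86 / 92% | 80-89% (range over ρ) | 90 / 97 / 99.9% |

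The within-child analysis is repeated-measures ANOVA in the first two rows and a paired test in the third. In the linear case one-way ANOVA keeps 67/85 = 79%, 64/96 = 67% and 62/99.8 = 62% of the attainable power.

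**Smaller effect.** For a linear fall of 5 points over 5 visits, one-way ANOVA has 11 / 5 / 2% power against 27 / 37 / 59% for repeated-measures ANOVA. It keeps 11/27 = 41%, 5/37 = 14% and 2/59 = 3%.

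**The case against.** The strongest reply is that ANOVA is not in itself an independent-groups test. With child as a factor it is a valid repeated-measures analysis, the protocol does not say one-way, and a separate analysis plan could settle the model. This stands in part: the one-way reading is an inference. It rests on the fallback, since Kruskal-Wallis is the counterpart of one-way ANOVA and Friedman that of the repeated-measures form, and on the absence of any child term. The reply does not rescue Kruskal-Wallis, which Section 10 fixes by name and a later plan would have to contradict.

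A second reply is that the shortfall against 80% power depends on assumptions. This stands. Section 10.3 does not say whether one overall test or a comparison of baseline with single visits is meant, and no time course is given. With an early sustained fall or two time points, one-way ANOVA reaches about 80% or more at the planned difference. The power loss must be given as a range.

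A third is that a conservative test on scales other than the primary one does little harm. The direction and scope are correctly described, but a test that misses real change is still a poor choice when the same data support a valid one.

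**Conclusion.** The point holds in a limited form. Kruskal-Wallis is wrong for this design, and ANOVA is under-specified and probably meant as one-way. Under positive, equal within-child correlation of 0.3 to 0.7, the true type I error with five visits is about 1% down to nearly 0%, and with two time points about 2% down to about 0.1%. The power cost at a difference of 10 runs from under 10 percentage points (two time points) to nearly 40 (linear fall, ρ = 0.7, one-way ANOVA). At zero correlation there would be no such cost.

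Three stronger conclusions that a reader might draw are not supported:
- That most of the power is lost. At the protocol's own difference of 10, ANOVA keeps at least about three fifths of it. More than half is lost only for smaller effects, such as a linear fall of 5 points.
- That the tests could produce a false claim of benefit. The error goes the other way.
- That every before-after comparison, or the primary analysis, is affected. Sections 10.3 to 10.5 cover SCORAD, POEM and DLQI only; IGA is the primary endpoint in 9.1.3 and has no test among them.

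**What to change.** In 10.3, 10.4 and 10.5, replace the ANOVA and Kruskal-Wallis pair with a within-child analysis: repeated-measures ANOVA, or a mixed model with visit as fixed and child as random effect. Name Friedman (several visits) or Wilcoxon signed-rank (baseline against one visit) as the non-parametric alternative. Check normality on within-child changes or model residuals, not on the raw scores. State whether the comparison is one test over all visits or baseline against a named visit.

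The cost is about one sentence per analysis, made before the data are analysed. Visits, measurements and data are unchanged. The 33 children still suffice for a difference of 10: with SD 13.576 at each visit, a paired comparison at 80% power needs (1.96 + 0.84)² × 2(1 − ρ) × 13.576² / 10², which is about 21, 15 or 9 children at ρ = 0.3, 0.5 or 0.7.

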- a) Could moisturiser with tocotrienol rich composition (REMDII[®] Sensitive, Malaysia) improve severity of atopic dermatitis of children with mild to moderate atopic dermatitis?
- b) What is the extend of baseline changes in IGA, SCORAD, IDLQI, PO-SCORAD, HR-USI, TEWL, skin color and pruritus score in children upon usage of REMDII[®] Sensitive?
- c) How well would children tolerate REMDII[®] Sensitive?

6. Research objectives and hypotheses

General objective

To assess the effectiveness and safety of a moisturiser containing tocotrienol rich composition (REMDII[®] Sensitive, Malaysia) on children with mild-to-moderate atopic dermatitis.

Specific objectives

- To assess the effectiveness and safety of REMDII[®] Sensitive as a supplement in mild-to-moderate atopic dermatitis in children based on the changes of IGA score and SCORAD.
- To assess correlation between patient-assessed PO-SCORAD and clinicianassessed IGA and SCORAD in children after 12 weeks of treatment using REMDII[®] Sensitive.
- To assess the changes in IDLQI.
- To assess the changes in patients' assessment of pruritus (based on a 100 mm Visual Analogue Scale and 0-3 ordinal scale).

- To assess the changes in skin properties, specifically high resolution ultrasound skin imaging (HR-USI), transepidermal water loss (TEWL) and skin color in children before and after application of REMDII[®] Sensitive.
- To assess the frequency of need for rescue medication in the event of an atopic dermatitis flare.

Hypotheses

Null: REMDII[®] Sensitive does not improve severity of atopic dermatitis of children with mild to moderate atopic dermatitis.

Alternative: REMDII[®] Sensitive significantly improves severity of atopic dermatitis of children with mild to moderate atopic dermatitis.

7. Literature review

Eczema is a general term used to describe numerous forms of epidermal inflammation or irritation that occurs regardless of gender, race and age. Among the various types of eczema, the most prevalent type is atopic dermatitis (AD). Currently, the prevalence rate of AD in children and adolescents was 15.0-20.0%, regardless of regions (Asher et al., 2006; Baek et al., 2013). Eczema poses significant impact and inconveniences to the patients' quality of life and health-care resources, mainly because of sleep deprivation and demoted self-esteemed (due to itchiness, scarring, lichenification, peer pressure and time to care), that would in turn affects the child's growth and development.

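### Sections 10.3–10.5 test for any difference among five visits, so P < 0.05 does not show that week 12 differs from baseline

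*Protocol*

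**What the plan says.** The protocol's section 10 names one type of test for three scales.

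- SCORAD (10.3): "Comparison of SCORAD index between baseline and follow-up visits (if data is following Gaussian distribution, ANOVA will be used".
- POEM (10.4): "Comparison of POEM between baseline and follow-up visits (if data is following Gaussian distribution, ANOVA will be used".
- DLQI (10.5): "Comparison of DLQI between baseline and follow-up visits (if data is following Gaussian distribution, ANOVA will be used".
- The alternative in each case: "If it is not following Gaussian distribution, Kruskal-Wallis test will be used".

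Section 10.1 sets the threshold, "A value of P < 0.05 is considered statistically significant", and the reporting format, "Descriptive date will be expressed as mean ± standard deviation (SD) unless otherwise stated". Section 9.1.10 requires five visits and 12 weeks of use. Nothing in section 10 names a contrast, a deciding visit, a within-child change or a confidence interval.

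The questions the trial sets itself are more specific. The alternative hypothesis in section 6 is that the product "Sensitive significantly improves severity of atopic dermatitis of children with mild to moderate atopic dermatitis". Research question (b) in section 5 asks "What is the extend of baseline changes in IGA, SCORAD, IDLQI, PO-SCORAD, HR-USI, TEWL, skin color and pruritus score in children". Section 9.1.3 defines most endpoints as changes from baseline. The primary one is change in IGA, which 10.3–10.5 do not mention.

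**The concern.** ANOVA or Kruskal-Wallis over five visits asks whether any visit differs from any other. The protocol asks whether disease has improved from baseline, and by how much, over 12 weeks. These questions can have different answers. A shift confined to one intermediate visit can produce a small P value although week 12 is no different from baseline.

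This matters because the trial has a single arm, so change within the child is the only efficacy evidence. Scores at individual visits may also move for reasons unrelated to a lasting effect, since flares are foreseen and treated with short courses of topical steroid (9.1.10.6). A significant omnibus P value could then be cited as support for a 12-week benefit that it did not test.

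The point is separate from whether the tests respect the pairing of visits within a child. A repeated-measures ANOVA or a Friedman test would be just as omnibus.

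**Working it through.** **Inputs from the protocol.** SCORAD difference 10 and SD 13.576 (9.1.8); 5 visits (9.1.10.1); significance level 5%, two-sided through z = 1.96 (9.1.8).

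**Assumptions.** Week 12 is the last visit (the flow chart is not shown). Data are normal with equal SD at each visit. The within-child correlation ρ is the same for every pair of visits, and since the protocol gives none it is taken as 0, 0.3, 0.5 and 0.7.

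**Step 1: the protocol's own figure.** 2 × (1.96 + 0.84)² × 13.576² / 10² = 2 × 7.84 × 184.308 / 100 = 28.90. With unrounded z values the result is 28.932, as printed. Rounding up gives 29, and 29 / 0.90 = 32.2 gives 33. The stated sample size reproduces, and 29 completers are used below.

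**Step 2: a transient shift.** Let the visit means differ from baseline by 0, 0, −10, 0, 0, so that week 12 equals baseline. The overall mean is −2, and the sum of squared deviations is 8² + 4 × 2² = 80.

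For repeated-measures ANOVA the noncentrality is λ = 29 × 80 / [184.308 × (1 − ρ)], with 4 and 112 degrees of freedom. The one-way ANOVA and Kruskal-Wallis rates come from simulation (20,000 trials per scenario).

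| ρ | λ | Repeated-measures ANOVA | One-way ANOVA | Kruskal-Wallis | Week 12 vs baseline, paired t |
|---|---|---|---|---|---|
| 0 | 12.6 | 80% | 81% | 78% | 5% |
| 0.3 | 18.0 | 93% | 80% | 77% | 5% |
| 0.5 | 25.2 | 99% | 81% | 77% | 5% |
| 0.7 | 42.0 | >99.9% | 82% | 77% | 5% |

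The 5% is both directions together. The contrast declares an improvement in 2.4–2.7% of simulated trials.

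**Step 3: precision of the change.** The SD of a within-child change is 13.576 × √[2(1 − ρ)]. The 95% CI half-width is t(0.975, 28) = 2.048 times that SD, divided by √29.

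| ρ | SD of change | Half-width (SCORAD points) |
|---|---|---|
| 0 | 19.2 | 7.3 |
| 0.3 | 16.1 | 6.1 |
| 0.5 | 13.6 | 5.2 |
| 0.7 | 10.5 | 4.0 |

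The SDs at each visit are identical in all four rows, so reporting them cannot tell a reader which row applies.

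**Step 4: power for a real effect** (noncentral F and t; ρ = 0.3 / 0.5 / 0.7).

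| True pattern | Omnibus repeated-measures ANOVA | Week-12 contrast |
|---|---|---|
| Linear, 6 points by week 12 | 38 / 53 / 78% | 49 / 63 / 84% |
| Linear, 10 points by week 12 | 85 / 95 / 99.8% | 90 / 97 / 99.9% |
| 6 points from first follow-up, sustained | 48 / 65 / 88% | 49 / 63 / 84% |
| 10 points from first follow-up, sustained | 93 / 99 / >99.9% | 90 / 97 / 99.9% |

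The power rates depend only on the size of the change, so they apply equally to a worsening of the same shape.

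**The case against.** Two stronger readings are tempting, and the documents support neither.

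*A reader might infer that the tests are faulty because they would also be significant for a worsening.* Any two-sided test is, and the protocol sizes the trial two-sided. For a steady 10-point worsening the week-12 contrast rejects more often than the repeated-measures omnibus test (90 / 97 / 99.9% against 85 / 95 / 99.8%). The planned means show the direction, section 11 speaks of positive changes, and nothing says a worsening would count as success.

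*A reader might infer that the plan gives no effect size.* Mean ± SD at each visit gives the mean change by subtraction, among children seen at both visits. Only its precision is missing.

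Other objections carry some weight:

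- The wording could mean baseline against each follow-up visit in turn. That is possible, but the choice of ANOVA and Kruskal-Wallis with no pairwise step favours the omnibus reading. On the other reading the deciding visit would still be unnamed.
- A separate analysis plan may supply contrasts and intervals. The point here is not that detail is absent, but that the tests the protocol does name do not match its question.
- Nothing in the protocol supports a cohort-wide 10-point shift that returns exactly to baseline. It is an illustration that borrows the protocol's planning difference, not a forecast.
- The power advantage of the contrast holds for gradual change only. Where improvement is early and sustained, the omnibus test is similar or slightly better.
- The three scales are not the primary endpoint, and POEM is not among the endpoints in 9.1.3. Calling these analyses confirmatory would be misplaced.

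**Conclusion.** The concern holds in this limited form: as written, significance in 10.3–10.5 shows that some visit differs from some other, and does not show that week 12 differs from baseline. In the illustrative one-visit case the named tests are significant in roughly four trials in five, and respecting the pairing raises that to 93–100% at correlation 0.3 to 0.7, against 5% for a direct contrast. These rates rest on the protocol's SD, 29 completers, normal data and equal correlation between visits.

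Mean ± SD per visit partly answers research question (b), but leaves the uncertainty of the change unstated: the half-width could be anywhere from 4.0 to 7.3 points over the assumed correlations.

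This is an inexpensive improvement to secondary analyses, not a defect that invalidates the trial.

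**What to change.** For each outcome compared in 10.3–10.5:

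- Make the main comparison the within-child change from baseline to week 12, using a paired t-test or, if the changes are clearly non-normal, a Wilcoxon signed-rank test.
- Report the mean or median change with a two-sided 95% CI, and claim improvement only if the whole interval lies on the improvement side.
- Keep the comparison across all visits as a description of the time course.
- State that these are secondary analyses, and add the same week-12 change as the analysis of the IGA primary endpoint.

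The cost is wording in section 10, with no new data or visits. Two things are given up: effects seen only at intermediate visits no longer count as positive, and if improvement is early and sustained the omnibus test would have had similar or slightly higher power (at most about 4 percentage points in the cases shown).

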9.1.3 Endpoints

Primary endpoint: Change from baseline the severity of atopic dermatitis – IGA score.

Secondary endpoints:

- Changes in SCORAD
- Changes from baseline the
 - IDQOL & CDLQI
 - PO-SCORAD
 - Pruritus score (VAS/ ordinal)
 - Frequency of rescue treatment needed
 - High resolution ultrasound skin-imaging (HR-USI), skin color & Transepidermal Water Loss (TEWL)
- Correlation between SCORAD index and PO-SCORAD or IDLQI at each baseline and follow-up visit and absolute changes from baseline.
- Efficacy and safety assessment of the study product.

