- 9.1.10.11Initial weight of cream provided to subjects will be recorded and weighed.
- 9.1.10.12Subjects will be required to pay their visit to the study site, as stipulated, which takes about 45 minutes for each visit.
- 9.1.10.13Measurement of atopic dermatitis severity using IGA and SCORAD index will be conducted. DLQI will be answered by subjects at each visit too.
- 9.1.10.14Measurement of high resolution ultrasound skin-imaging (HR-USI), skin color and transepidermal water loss (TEWL) will be conducted using DermaLab® Series SkinLab Combo (DermaLab®, Denmark).

- 9.1.10.15Subjects need to submit the old bottles of cream to investigator where they will be weighed in every visits. New cream will be provided to subjects, when necessary, in which the weight will be recorded too.
- 9.1.10.16Subjects also have to submit their diaries to investigator. New sets of diaries will be provided to subjects.
- 9.1.10.17All adverse events that happened throughout the study will be recorded.

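### The sole primary endpoint, change in IGA, has no analysis in Section 10, and the instruments analysed there do not match the endpoint list

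*Protocol*

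**What the plan says.** Section 9.1.3 gives a single primary endpoint: "Change from baseline the severity of atopic dermatitis – IGA score". Its secondary list opens with "Changes in SCORAD" and goes on to quality of life (named there as IDQOL and CDLQI), PO-SCORAD, pruritus, rescue treatment and skin measurements. It also includes "Correlation between SCORAD index and PO-SCORAD or IDLQI at each baseline and follow-up visit and absolute changes from baseline". The first specific objective in Section 6 judges effectiveness "based on the changes of IGA score and SCORAD".

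Section 10 then fixes the analyses:

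- 10.3: "Comparison of SCORAD index between baseline and follow-up visits"
- 10.4: "Comparison of POEM between baseline and follow-up visits"
- 10.5: "Comparison of DLQI between baseline and follow-up visits"
- 10.6: correlation of SCORAD with POEM or DLQI, at baseline only.

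Items 10.3 to 10.5 prescribe ANOVA if the data look Gaussian and Kruskal-Wallis otherwise. On collection, 9.1.10.13 has IGA and SCORAD measured, and adds that "DLQI will be answered by subjects at each visit too".

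**The concern.** A primary endpoint is the variable on which the trial's main conclusion is meant to rest. Here the section that allots tests to named instruments passes over it. It gives a test to a secondary endpoint, and another to an instrument that the rest of the readable protocol never mentions.

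An analyst who follows Section 10 would report no inference on IGA. An analyst who adds an IGA analysis later would have to choose the time point, the definition of change or response and the method without a prespecified rule, in an open-label, single-arm trial where the results are visible as they accrue. The same mismatch affects PO-SCORAD and the correlation endpoint, where the variables and visits in Section 10 differ from those in 9.1.3.

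**Working it through.** **Step 1: trace each instrument through the protocol.**

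| Instrument | Objectives (Section 6) | Endpoint (9.1.3) | Visit procedures (9.1.10, text) | Analysis (Section 10) |
|---|---|---|---|---|
| IGA | yes | primary | 9.1.10.13 | none |
| SCORAD | yes | secondary | 9.1.10.10, 9.1.10.13 | 10.3, 10.6 |
| PO-SCORAD | yes | secondary | not named | none |
| POEM | no | no | not named | 10.4, 10.6 |
| IDLQI | yes | in the correlation endpoint | not under this name | not under this name |
| IDQOL, CDLQI | no | secondary | not under these names | not under these names |
| DLQI | no | not under this name | 9.1.10.13 | 10.5, 10.6 |

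IGA is used in 0 of the four items 10.3 to 10.6. POEM occurs only in 10.4 and 10.6.

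**Step 2: compare the correlation endpoint with its analysis.** Section 9.1.3 pairs SCORAD with PO-SCORAD or IDLQI, at baseline and follow-up visits and for changes from baseline. Item 10.6 pairs SCORAD with POEM or DLQI, at baseline. The partner instruments differ in name and the follow-up and change components are gone. Section 6 also has an objective to correlate PO-SCORAD with IGA and SCORAD after 12 weeks. A baseline-only analysis cannot address it.

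**Step 3: check what the sample size supports.** Section 9.1.8 uses a SCORAD difference of 10, SD 13.576, 80% power and 5% two-sided significance:

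- With the printed z values: 2 × (1.96 + 0.84)² × 13.576² / 10² = 2 × 7.84 × 184.308 / 100 = 28.899.
- With unrounded z values: 28.932, the figure printed. This rounds up to 29.
- With 10% dropout: 29 / 0.90 = 32.2, so 33.

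The stated 33 is reproduced, but every input is a SCORAD quantity. The protocol gives no IGA effect size, SD or response rate, so power for IGA cannot be derived from it. For scale only, a paired two-sided 5% comparison with 80% power (normal approximation) detects a mean change of (1.96 + 0.84) / √29 = 0.52 SD of the change with 29 children, or 0.49 SD with 33. What that means in IGA grades is unknown.

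**Step 4: see whether 10.3 could simply be extended to IGA.** It could not. Kruskal-Wallis treats the visits as independent groups, whereas each child is measured repeatedly. The ANOVA in 10.3 is not specified as a repeated-measures one either. IGA is also ordinal, and 9.1.5.2 with 9.1.6.2 restricts its baseline value to 2 or 3.

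**The case against.** The best defence is that a separate statistical analysis plan may supply the IGA test. That would cover a protocol that was silent or general. It does not cover this one, because Section 10 carries the title of an analysis plan and names instruments and tests one by one. A later plan that followed it would inherit the mismatch, and one that corrected it would contradict the protocol. By contrast, Section 10 says nothing on pruritus, rescue treatment or the skin measurements. That silence could be left to a later document and is not part of this point.

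Several stronger readings are tempting, and the protocol does not support them:

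- **That the trial cannot answer its primary question.** The hypotheses concern severity in general, and SCORAD, which is tested, measures severity. What lacks a test is the IGA endpoint.
- **That success may be claimed on either IGA or SCORAD, inflating the type I error.** No section states an either-or rule. Sections 6 and 11 join the two with *and*, and requiring both would not inflate the error.
- **That the DLQI analyses concern something outside the endpoints.** DLQI is collected at each visit and is plausibly shorthand for the infant and children's versions. This is a naming conflict, weaker than the POEM error.
- **That 10.5 pools different questionnaires.** It says nothing about pooling.
- **That POEM will have no data.** The visit schedule is in Figure 3, which could not be read here. The text of 9.1.10 does not name PO-SCORAD either, so its silence cannot be held against POEM alone.

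**Conclusion.** The point holds and should be corrected before analysis. The only primary endpoint has no analysis in the section that assigns them. POEM is analysed without being an endpoint, PO-SCORAD is an endpoint without an analysis, and 10.6 departs from 9.1.3 in both instruments and time points. The quality-of-life questionnaire appears as IDLQI, IDQOL, CDLQI and DLQI.

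The defect is a mismatch within the protocol, so its size is that none of the four analysis items addresses the primary endpoint. No error rate or loss of power can be attached to it, because the protocol gives neither a decision rule linking IGA and SCORAD nor any planning figure for IGA. The statements about visit procedures rest on the text of 9.1.10 without Figure 3.

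**What to change.** 1. Add a primary analysis to Section 10: within-child change in IGA from baseline to week 12, by a method for paired ordinal data. The Wilcoxon signed-rank test is one suitable choice. Report with it the proportion improving by at least 1 grade and its exact 95% confidence interval.
2. Label the SCORAD comparison in 10.3 as secondary.
3. Replace POEM with PO-SCORAD in 10.4 and 10.6, and confirm that PO-SCORAD is collected at the visits, naming it in 9.1.10.
4. Extend 10.6 to the instruments and time points in 9.1.3, and reconcile it with the 12-week correlation objective in Section 6.
5. Use one consistent set of names for the infant and children's quality-of-life questionnaires in Sections 6, 9.1.3, 9.1.10.13, 10 and 11, and analyse each separately.
6. State in 9.1.8 that 33 rests on SCORAD and that power for IGA was not calculated.

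The IGA part needs only wording: baseline IGA is required for eligibility and 9.1.10.13 already has IGA measured. Two costs remain open. If PO-SCORAD is not on the visit schedule, it must be added. Whether 33 children are enough for IGA cannot be judged until the sponsor supplies a planning assumption for it.
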